- Provider views about impacts on the service and trial procedures, assessed through qualitative interviews with 15 key staff in total (3 per site), sampling those who have roles in facilitating the study in each setting (e.g. receptionists, practice managers, nurses, midwives, doctors and pharmacists) (see Topic Guide). Questions to be explored include:
 - Are recruitment procedures acceptable to staff?
 - How might recruitment procedures be improved, to optimise recruitment to a fullscale trial?
 - What are staff views on the feasibility and usefulness of a contraception decision website in each clinic setting?

9. SAMPLE SIZE and RECRUITMENT

The original target sample size of 80 participants in each of the five settings was based on estimating an expected follow-up rate at 6 months of 70% to within 10% precision (95% Cl 60% to 80%) for each setting. This sample size also provided 80% power to detect a significant difference (at the 5% level) in the follow-up rate between two settings if the true difference is 22% (e.g. 59% vs. 81%). By pooling data across settings this sample size also provides 80% power to detect a significant difference (at the 5% level) in the follow-up rate between the follow-up rate between the intervention and standard arms if the true difference is 15% (e.g. 62.5% vs. 77.5%). The expected follow-up rate is based on a previous sexual health study that recruited and followed-up the participants online (Sex Unzipped).

Funder-approved amendment to sample size:

A further 530 participants are to be recruited from one existing site, though recruited in a different way (from the central booking system). Together with the original target size this

leads to a total of 930 participants. This new total sample size is calculated to provide power to assess the effect of the intervention on the revised primary outcome which is uptake of LARC at follow-up. Specifically, assuming a follow-up rate of 70%, this sample size provides at 82% power to detect as significant (at the 5% level) an increase from 35% (control group prevalence) to 47% in LARC use due to the intervention.

The recruitment period of 6 months is based on:

- the volume of patients attending each of the study sites, which is high i.e. hundreds or dozens of women per week in four sites GP, SRH, maternity service and bpasand at least 30 women per month in the pharmacy,

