10.4. Questionnaire Measures

Demographics:

Participants will be asked to complete a demographic questionnaire at baseline, which will assess relationship status, age, employment status, and ethnicity (See Demographic questionnaire).

Contraception questionnaire:

Participants will be asked to complete a questionnaire at baseline, and at 3 and 6 month follow-up to assess what contraceptive methods, if any, they are using currently or have used before (baseline) or since enrolling in the study (at follow-up). Participants who are currently using contraception will be asked how satisfied they are with the method. At follow-up only, participants will be asked if they have had a pregnancy and, if they have, the outcome of the pregnancy (ongoing, gave birth, miscarried, terminated, or prefer not to say). All participants are asked at baseline, 3 and 6 months, whether they have been told by a doctor or other health professional that they have a sexually transmitted infection.

Service use related to contraception and sexual health:

Participants will be asked to specify where they go to get their contraception and if they pay for it themselves.

Interaction with the intervention

In order to assess engagement with the intervention (and whether this is related to outcome), we will record website usage. The software used will record the number of times

each user visits the site, the amount of time spent on the site, the pages visited, and the amount of time spent on each page.

Methods to protect against sources of bias

Participants will provide baseline data on the tablet device before randomisation. Once eligibility for the study is established, and baseline data are collected, allocation to intervention or control group will be determined from the randomisation list, and this will not be changeable by participants or researchers. Subsequent outcome data will be collected online using an emailed weblink to the online outcome questionnaire. Data will be saved on an encrypted server, and data exported will be identifiable by study ID numbers only. Most data collection procedures are therefore automatically blind to allocation to intervention or control group, since they are automated. Sealed envelope will grant access to group allocation only to those who need to know, to for data analysis.

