To maximise retention, we plan to make phone calls to non-responders (conducted by the trial co-ordinator), and it could be that group allocation is revealed by participants during the phone call. Data analysis for the primary outcomes will be conducted by statisticians who are blinded to group allocation.

[figure not shown]
Maximising retention

Our experience in the Sexunzipped and Men's Safer Sex online RCTs indicates that follow-up by email is acceptable to participants with email accounts. The Txt2Stop smoking reduction trial obtained their excellent follow-up using multiple methods of contacting people;²⁰ similar methods will be used for the present study:

- 1. Automated Email, with 3 further follow-up emails at weekly intervals
- 2. 2 text messages at the same time as the last two emails
- 3. One phone call a week after the final email
- 4. One final questionnaire by post

We will offer participants a £10 voucher for filling in the online questionnaire at 3 months, and a further £10 for the 6 month follow-up questionnaire. Incentives (a shopping voucher) will be sent by email.

Figure 2 Follow-up procedures

Lost to follow-up

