The primary outcome of LARC use at 6 months will be analysed among women in need of contraception (not pregnant or currently trying to become pregnant) and the primary outcome of satisfaction with method will be analysed among women who are using a method at 6 months. The primary outcome of LARC use at 6 months will be analysed stratified by LARC use at baseline, leading to three intervention effects: the effect in baseline LARC users, the effect in baseline non-users, and the overall effect adjusted for baseline LARC use. In the event that over 90% of baseline LARC users in the control arm are using a LARC method at 6 months (or no longer need contraception) then the primary effect measure for this outcome will be the intervention effect in non-LARC users. If conversely fewer than 90% of baseline LARC users in the control arm are using a LARC method at 6 months then the primary effect measure will be the overall adjusted intervention effect. A further subgroup analysis will be conducted for both primary outcomes to assess, based on testing an interaction term, whether the effect of the intervention varies by setting.

Primary comparisons between arms will be based on multiple imputation where outcomes at 6 months are imputed based on outcomes at 3 months for those participants who completed the 3 month outcome questionnaire but failed to complete the questionnaire at 6 months.

Health Economics

The primary analysis will be a budget impact analysis of the website and contraception reporting the total costs to each payer (NHS (primary care versus secondary care), local government, private and out of pocket). This will reported as total cost of contraception and pregnancy outcomes for a range of different population sizes. The analysis will conform to the ISPOR good practice guidelines for budget impact analysis.²¹

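### The control arm's own 6-month LARC use selects the primary effect measure, by a rule that tilts modestly towards the website, strains the blinded analysis and can point to both measures at once

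*Protocol*

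**What the plan says.** Section 10.5 of the protocol stratifies the analysis of LARC use at 6 months by LARC use at baseline. It yields three effects: in baseline users, in baseline non-users, and overall with adjustment for baseline use. A threshold then decides which is primary.

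- First condition: "In the event that over 90% of baseline LARC users in the control arm are using a LARC method at 6 months", where women whose need for contraception has ended also count towards the 90%, "then the primary effect measure for this outcome will be the intervention effect in non-LARC users".
- Second condition: "If conversely fewer than 90% of baseline LARC users in the control arm are using a LARC method at 6 months", the overall adjusted effect is primary. Women whose need has ended are not mentioned here.

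Section 10.4, under the methods to protect against bias, says: "Data analysis for the primary outcomes will be conducted by statisticians who are blinded to group allocation". It also says: "Sealed envelope will grant access to group allocation only to those who need to know". No section says who evaluates the 90% rule, when, or how blinding is kept while that is done.

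Section 9 sizes the trial for "the revised primary outcome which is uptake of LARC at follow-up". The enlarged recruitment "leads to a total of 930 participants", with 70% followed up, 35% LARC use in the control group and 47% in the intervention group, and a stated power of 82%. That calculation covers all participants followed up, with no split by baseline use.

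**The concern.** The control outcomes that trigger the rule are also half of the data in the baseline-user stratum of the overall estimate. If control users happen to do badly, that stratum is kept and its chance difference flatters the website. If they happen to do well, the stratum that would have counted against the website is dropped. The effect in non-users comes from different women, so it carries no bias in the other direction to offset this.

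Two further problems follow from the wording. The trigger is a proportion in a named arm, which analysts blinded to allocation cannot always identify. And because the two conditions are not mirror images, there are results for which the protocol names no primary measure, or two. At stake is whether the main LARC result rests on one quantity known in advance.

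**Working it through.** **The plan's own figure.** Inputs from section 9: 930 × 0.70 = 651 followed up, or 325.5 per arm at 1:1 (the Summary gives 1:1 for the original sites; assumed for all), 35% against 47%, 5% level taken as two-sided. The mean rate is 0.41.

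z = [0.12 − 1.96·√(2·0.41·0.59/325.5)] / √[(0.35·0.65 + 0.47·0.53)/325.5] = (0.12 − 0.0756)/0.0383 = 1.16, so power is 87.7%.

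The stated 82% is not reproduced and is conservative; this does not bear on the point. The design effect is ln(0.47/0.53) − ln(0.35/0.65) = 0.50 log OR.

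**Assumptions for the rule.** The documents give neither the share of baseline LARC users in this trial nor their retention. Section 6 reports 24% LARC use in women under 30 at specialist community services, so 24% is the central value, with 10-40% as the range. Retention was varied from 80% to 95%. At 24% users and 90% retention, a 35% overall rate implies (0.35 − 0.24·0.90)/0.76 = 17.6% in non-users. The control arm then has about 0.24 × 325 = 78 baseline users.

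**Simulation under no effect.** There were 60,000 trials per scenario with 325 per arm. The overall effect was the common odds ratio adjusted for baseline use, the non-user effect was the odds ratio in that stratum, and the 90% rule was applied to observed control retention. Missing data and imputation were not modelled. With q the chance that one arm exceeds 90%, the arms fall on opposite sides with probability 2q(1 − q).

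Results with 24% baseline users:

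| True retention | Non-user effect chosen (q) | Mean bias, log OR | False positive favouring website | False positive favouring control | Two-sided | Arms split by 90% |
|---|---|---|---|---|---|---|
| 80% | 1% | +0.002 | 2.4% | 2.3% | 4.7% | 2% |
| 85% | 10% | +0.011 | 2.7% | 2.0% | 4.7% | 18% |
| 88% | 30% | +0.022 | 3.0% | 1.8% | 4.8% | 42% |
| 90% | 51% | +0.025 | 3.1% | 1.8% | 4.9% | 50% |
| 92% | 75% | +0.020 | 3.1% | 2.0% | 5.1% | 38% |
| 95% | 97% | +0.003 | 2.7% | 2.4% | 5.1% | 7% |

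With the overall effect fixed in advance, bias is within 0.002 log OR and each one-sided error is 2.4-2.6%.

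**Range.** A repeat with a Mantel-Haenszel test stratified by baseline use, at shares of 24% and 40% (non-user rate 20% at the 40% share) and retention of 88-92%, gives about 3.0-3.3% favouring the website and 1.6-2.0% favouring control. The latter falls to 1.4% if the non-user rate is only 10%. The arms split in 32-50% of those trials. A 40% share is an upper bound: 0.40 × 0.90 = 36% already exceeds the 35% overall rate in section 9. At 90% retention, mean bias is +0.011 with 10% users and +0.047 with 35%.

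**Scale.** 0.025/0.50 = 5% of the design effect. On a 35% base this is about 0.35 × 0.65 × 0.025 = 0.6 percentage points, against the 12 targeted.

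**The two conditions.** Suppose 85% of control baseline users are on LARC and 7% no longer need contraception. The first condition reads 85 + 7 = 92%, above 90%. The second reads 85%, below 90%. Both are met, and two effects are primary. With 78 control baseline users and these as assumed true rates, this happens in about 63% of trials. A result of exactly 90% meets neither condition as worded.

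**The case against.** The rule has an evident purpose: if nearly all LARC users continue, the website has little room to change that stratum. The threshold and both candidate effects are fixed in the protocol, and all three effects are produced whichever is primary. A reader might infer that the measure is picked ad hoc once results are known. The text does not support that; the choice depends on the data but is pre-written.

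A reader might also infer a large inflation of type I error. The calculation does not show one. Two-sided error stays at 4.4-5.1%, and the tilt is confined to retention near 90%, a value the documents do not give. Higher figures arise only by looking within one branch: at 92% retention, given that the overall effect is chosen, the error favouring the website is about 4.2-6.1%. That branch is chosen in only about 20-25% of such trials.

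Nor is it right that blinded statisticians can never apply the rule. Coded arms suffice when both lie on the same side of 90%, and section 10.4 allows allocation to be released to those who need it, so someone outside the blinded team could evaluate the trigger. The data analysis plan promised in section 10.11 could set that up. What stands is that the protocol gives no such step, and that near 90% the arm label often decides the primary result.

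Exactly 90% is a minor gap, since it needs a control stratum whose size is divisible by 10. Counting women whose need has ended may be deliberate. Its absence from the second condition is still a contradiction about which effect is primary.

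**Conclusion.** The point holds in a limited form, and the plan should be changed. A pre-written, data-dependent rule lets the control arm's 6-month outcome select the primary effect measure. It moves one-sided error from 2.5% each way to about 3.0-3.3% favouring the website and 1.6-2.0% favouring control. Average bias is about +0.02 to +0.025 log OR at 24% baseline users. These figures assume 24-40% baseline users and 88-92% true retention, and they largely vanish at 80% or 95%. The statistical harm is modest.

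The textual faults do not depend on those assumptions. The rule can require the control arm to be identified in an analysis described as blinded, and its two conditions can name both effects or neither.

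The section 9 sizing does not cover the non-user branch. As an illustration, 35% against 47% in non-users alone has about 78% power with 24% baseline users (84% with 10%, 71% with 35%), though the non-user rate would differ from 35%.

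**What to change.** Delete the 90% rule from section 10.5. Name the overall effect adjusted for baseline LARC use as the single primary effect measure for LARC use at 6 months; it is the closest match to the all-participant comparison sized in section 9. Keep the effects in baseline users and in non-users as pre-specified secondary estimates.

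The cost is one paragraph, agreed before any 6-month outcome is seen by arm. The downside is slight dilution of the primary effect if nearly all baseline users continue, but the non-user effect is still reported.

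If the sponsor prefers to keep a rule, base it on retention pooled over both arms and evaluated blind. Use one definition of retention in both conditions, and state which side exactly 90% falls on.

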4. SUMMARY

Reducing unintended pregnancy is a national and global priority, and improving women's choice of contraception is a vital step. There are many myths, misunderstandings and concerns about contraception, and increasingly women turn to online resources for information on healthcare.

The aim of the study is to develop and test the feasibility of an online trial of a website to increase the acceptability, uptake and adherence to long-acting reversible contraceptive (LARC) methods in young women. LARC methods include the intrauterine device (IUD), intrauterine system (IUS), subdermal implant (SDI) and depo injection.

In Phase 1 of this study (completed) we developed a self-guided website that presents recommended contraceptive options in response to women's preferences. The website will be presented on a touch-screen tablet computer in clinic waiting areas or pharmacy consulting areas.

In Phase 2 (this study), we will assess feasibility of an online trial of the contraception choice website in five sites:

An NHS sexual health service (Margaret Pyke Centre, MPC)

A local general practice

A maternity service (Ashford & St Peter's Hospitals NHS Foundation Trust)

A community pharmacy (Greenlight)

An abortion service (bpas)

Phase Two will take 15 months including:

- Conducting a randomised pilot trial across the five settings
- Conducting a qualitative process evaluation of the website, of NHS implementation issues and of research procedures
- Analysis, reporting and dissemination of study findings
- Preparation of outputs, including a protocol for a definitive RCT to increase uptake and adherence of LARC that is informed by both quantitative and qualitative findings In each setting we will recruit 80 women aged 15-30 years (40 randomised to intervention and 40 to control) and follow them up by online questionnaire at 3 and 6 months (or 2 months after delivery for post-partum women).
- *Funder-approved amendment to recruitment*. In addition to the above, we will recruit 530 more women from one site only, the Margaret Pyke Centre, via their Central (telephone) Booking System. Women requesting an appointment for

contraception will be invited to go online and enter the trial before they attend their appointment.

Data collection:

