7. AIM AND OBJECTIVES

The aim of the study is to develop and test the feasibility of an online trial of a website to increase the acceptability, uptake and adherence to long-acting reversible contraceptive (LARC) methods in young women. LARC methods include the intrauterine device (IUD), intrauterine system (IUS), subdermal implant (SDI) and depo injection.

The objectives are:

Phase 1 (completed)

1. To systematically review evidence on individual level education or decision aid interventions relating to acceptability, uptake and adherence to LARC, including underpinning theories and user and provider views.

2. To obtain the views of contraceptive service users and providers in six settings (general practice, sexual & reproductive health services, abortion services, maternity services and community pharmacies) relating to access, acceptability, uptake and adherence to LARC

3. To apply the information from objectives 1 and 2 to identify the key design issues and content for an interactive digital intervention (website) and an appropriate comparator

4. To co-develop the website with young women (through focus groups and interviews) and healthcare professionals (through an expert workshop)

Phase 2

5. To conduct a randomised pilot trial of the website in five different service settings (general practice, sexual & reproductive health service, abortion service, maternity service and community pharmacy).

6. To conduct a qualitative process evaluation with women and clinic staff, to assess the acceptability of the trial procedures, women's views of the intervention itself and implementation considerations.

7. To write a protocol for a definitive trial of an interactive digital intervention (website) to improve informed choice of contraception and the acceptability, uptake and adherence to LARC methods in young women.

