It is routine practice at the Margaret Pyke Centre to send patients a text message to confirm their appointment. For this study, women who have booked a contraceptive appointment will be sent an additional text informing them that the clinic is taking part in a study to improve information about contraception, and inviting them to go online (by clicking on a hyperlink) and see if they want to take part in the study before they attend their appointment. Clicking on the hyperlink will take women to the trial website from where all procedures are the same as above.

Randomisation procedures

A randomisation list will be generated for the trial by a random number based algorithm in the computer software Stata. This list will be incorporated into the trial software programme before the trial begins, to allocate all participants to either the intervention or control condition. This allocation will be unalterable. Allocation will be concealed until the point of allocation, which will be immediate.

Participants allocated to the control condition will be notified that they have not been selected to view the intervention and told they will be contacted again in 3 and 6 months (or two months post-partum) to gather follow-up data. Those allocated to the intervention condition will be directed to the intervention website. Patients may stop viewing the website whenever they wish, and buttons will be included on the web pages to exit, recording whether they exiting because they want to (e.g., if they're bored), or if they are being called in to see the clinic staff. This data will be recorded, in order to give information about feasibility of website usage in practice.

For patients recruited through the MPC Central Booking Office there will be a variable interval of a few days before they attend their clinic appointment. All other registration and

intervention viewing is designed to take place in the waiting room, whilst patients are waiting to be seen by the clinic staff. This is designed to mimic how the intervention may work in practice – it can be offered to patients on arrival, so that they can complete activities in the time that they are waiting (often up to an hour).

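### The only planned interaction test is by setting, but since the amendment the sexual health clinic's cell mixes two delivery routes (87% booking route), so route and setting cannot be separated

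*Protocol*

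**What the plan says.** Section 7 describes a "randomised pilot trial of the website in five different service settings" and lists them as general practice, sexual and reproductive health, abortion, maternity and community pharmacy. Section 9 gives the starting point as "The original target sample size of 80 participants in each of the five settings". The amendment adds the booking-route women; in the words of section 4, "we will recruit 530 more women from one site only, the Margaret Pyke Centre". Section 9 notes that these women are recruited differently but assigns them to an existing site, and the sum "leads to a total of 930 participants". The booking route is never listed as a setting of its own.

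The two routes deliver the website at different times. Under the randomisation heading in section 10.3, for women "recruited through the MPC Central Booking Office there will be a variable interval of a few days" before the clinic visit. Everyone else is meant to register and view the website in the waiting room. Section 10.2 explains why: delivery is designed to begin in clinic, when the patient is already thinking about her health.

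Section 10.5, refocused after the amendment on effect sizes for contraceptive outcomes, has one interaction test, for both primary outcomes: "based on testing an interaction term, whether the effect of the intervention varies by setting". For LARC use it also reports "the effect in baseline LARC users, the effect in baseline non-users, and the overall effect adjusted for baseline LARC use". No analysis by recruitment or delivery route is stated.

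**The concern.** The pilot is meant to inform a definitive trial, including where and how the website should be offered. On the plain reading of section 10.5, four settings consist only of waiting-room women, while the fifth consists mostly of women who go online before the appointment. If the effect looked different at the sexual health clinic, the planned analysis could not say whether the clinic or the route was responsible. A team designing the next trial would act differently on each: choose sexual health clinics in one case, or send the link ahead of the visit in any service in the other.

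**Working it through.** **Inputs.** From section 9: 80 women in each of five settings, 530 added, 70% follow-up, LARC use 35% (control) and 47% (intervention), 5% level. From section 4: 1:1 allocation for the first 400. Assumed: 1:1 for the 530 as well, two-sided testing, equal follow-up in both routes, and 35%/47% in every subgroup.

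**1. The plan's own figures.** 5 × 80 + 530 = 930, as stated. The 82% power does not reproduce: 930 × 0.7 / 2 = 325.5 per arm gives 87.7% for 35% v 47% (86.0% with continuity correction). That is a separate discrepancy on the cautious side and has no bearing here.

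**2. Composition of the cells.**
- Sexual health clinic: 80 + 530 = 610, which is 610/930 = 66% of the trial.
- Booking route within that clinic: 530/610 = 87%. Within each other setting: 0%.
- Booking route in the whole trial: 530/930 = 57%.

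**3. What a pure route effect would look like.** As an illustration, not a document figure, let the effect be 12 points by booking route and 0 on site in every setting.
- Clinic effect: (530 × 0.12 + 80 × 0)/610 = 0.104.
- Effect in each other setting: 0.
- Overall effect: 530 × 0.12/930 = 0.068.

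So 87% of a route difference appears as a clinic-versus-rest difference.

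**4. Precision of the possible contrasts.** The normal approximation for a difference between two risk differences uses V = 0.35 × 0.65 + 0.47 × 0.53 = 0.4766 and SE = √(V/nA + V/nB), where nA and nB are women followed per arm in each group. The difference detectable with 80% power is 2.80 × SE. Power for a difference d is Φ(d/SE − 1.96).

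| Contrast | nA v nB | SE | Detectable (points) | Power for 12 points |
|---|---|---|---|---|
| One 80-woman setting v another | 28 v 28 | 0.185 | 52 | 10% |
| Clinic (610) v one 80-woman setting | 213.5 v 28 | 0.139 | 39 | 14% |
| Clinic (610) v other four pooled (320) | 213.5 v 112 | 0.081 | 23 | 32% |
| Booking (530) v on-site (80), within the clinic | 185.5 v 28 | 0.140 | 39 | 14% |
| Booking (530) v all on-site (400) | 185.5 v 140 | 0.077 | 22 | 34% |

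For the 10.4 points in step 3, the clinic-versus-four contrast has power Φ(0.104/0.081 − 1.96), about 25%. The planned test across five settings spreads over four degrees of freedom and would probably do worse.

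**5. Reading the table.** The third and fifth rows are almost the same comparison: 530 of the clinic's 610 women are booking route, and 320 of the 400 on-site women (80%) are in the other four settings. Only the fourth row holds setting constant, and it is imprecise.

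**The case against.** The strongest reply is that the merging is inferred. Section 10.5 does not list the levels of setting, section 9 shows that the authors regard the 530 as recruited differently, and section 10.11 promises an analysis plan before database lock. That plan could make the booking route its own level. This stands as a caution, but the protocol itself chose the subgroup factor, defines five settings and places the 530 inside one of them.

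Four stronger readings are tempting and are not supported.
- A reader might infer that a route effect would be reported as a setting effect. With about 25% power in the illustration, a non-significant test is the likelier outcome, and the route effect would then be averaged into an overall estimate that is 57% booking route.
- A reader might infer that comparing all on-site women with booking-route women settles the matter with usable precision. That contrast is confounded with setting in its turn, and has only about 34% power for 12 points.
- A reader might infer that the trial's main result is biased. Women are individually randomised in both routes, so the overall comparison is unaffected.
- A reader might describe the booking route as viewing at home. The protocol says only that these women are invited to go online before the appointment.

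It is also fair to say that setting is not the only look at varying effects, since LARC effects by baseline LARC use are planned. Implementation by setting is further judged on recruitment, follow-up and qualitative work. Website usage will be recorded and may be related to outcome (section 10.4), and waiting-room women may revisit the site later, which softens the contrast between routes. None of this estimates the intervention effect by route.

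**Conclusion.** The point holds in limited form. As the protocol is written, the one interaction test uses a factor that mixes two delivery routes in one cell (87% booking route) and has a single route in the other four. A difference by route therefore could not be distinguished from a difference by setting, or could be missed because power is low. Only the interpretation of effect variation is affected.

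This rests on the five-setting reading, full recruitment to target, 70% follow-up in both routes and the section 9 LARC rates. Section 8 speaks of up to 80 women per site, and the LARC analysis is limited to women in need of contraception, so real precision is likely to be lower than tabulated. The figures are on the risk-difference scale, whereas section 10.5 plans logistic regression, and they cover LARC use only, not satisfaction.

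**What to change.** In section 10.5, define the interaction factor with six levels: the five settings restricted to on-site recruits (up to 80 each), and the booking-route women as a separate level. Report the intervention effect with its 95% confidence interval at each level, for both primary outcomes. This makes the on-site settings comparable with one another.

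Add the booking-versus-on-site contrast within the sexual health clinic, labelled exploratory, with a note that at 530 v 80 it detects only about 39 points with 80% power. If the pooled on-site versus booking-route contrast is also shown, state beside it that it is confounded with setting and has about 34% power for 12 points.

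The cost is wording plus one degree of freedom (five instead of four) in an exploratory test that is already weak, so the estimates and intervals should carry the message. The trial software must be able to identify each woman's entry route; the protocol does not say so explicitly, and this should be confirmed.
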